#### 7. Trial Hypotheses

The objective of the primary endpoint analysis is to demonstrate that the rate of the composite success endpoint in subjects with the Pyrocarbon HH is non-inferior to the rate observed in the Tornier Aequalis Post-Market Outcomes Study dataset. Formally, the hypothesis to be tested is:  $H_0: p \leq PG - \delta$ 

 $H_A: p > PG - \delta$ 

Where p is the proportion of subjects with a success for the composite success endpoint, PG is the performance goal, and  $\delta$  is the non-inferiority margin. The PG is derived from data for the Aequalis subjects with the appropriate indications and with two years of follow up data (or revision prior to two years). The PG and  $\delta$  being used for the hypothesis test take on the values of 0.85 (or 85%) and 0.10 (or 10%), respectively.

#### 8. Trial Success Criteria

The non-inferiority of Pyrocarbon HH will be evaluated by a two-sided 95% confidence interval for the success rate (p). The study will be considered a success if the lower bound of the confidence interval is greater than 0.75 (0.85 - 0.10).

### 9. Trial Design

This is a multi-center, prospective, single arm, investigational clinical study. The study will be conducted at up to 20 sites in the US. Each participating site will be encouraged to attempt implants in approximately 5 subjects in a 12 month time period, or until the enrollment limit is met. A subject is "enrolled" and count towards the enrollment limit of 190 subjects once the consent form is signed. A subject will count towards the limit of 157 subjects when inclusion/exclusion criteria are met (including unsuccessful and successful implantation of a PYC HH). Up to 157 subjects will have attempted implants with a Pyrocarbon HH to ensure at least 133 evaluable subjects are available for the primary endpoint analysis.

It is anticipated that this study will require approximately up to 24 months for subject enrollment. To ensure data are adequately distributed among sites and geographies, no more than 20% (n=31) of subjects may occur at a single site. Each site should attempt to implant 5 subjects within 12 months of activation. There is no minimum requirement for enrollments per site.

All enrolled subjects will be followed for at least 24 months (except for pre-operative screen failures). Study duration (first site activation to final subject follow-up) is expected to be approximately 4 years. If deemed necessary, subjects may be asked to return for additional visits beyond their final protocol visit to collect long-term data

Subjects who are enrolled and have a successful implant attempt (implant stable through wound closure) will have study assessments at 2 weeks, 3 months, 6 months, 12 months, 24 months, and annually thereafter (until the last implant attempt subject completes their 24 month visit) following surgery. Subjects will exit the study after the last implant attempt subjects completes their 24 month assessment unless it is determined, at the end of the study, to follow subjects long-term.

Subjects who are enrolled and have an unsuccessful implant attempt (attempt to implant the Pyrocarbon Humeral Head was not successful during the index procedure) will have annual post-op visits at 12 and 24 months in order to collect any available safety information. This also includes subjects who are excluded due to excessive glenoid reaming performed with the intent of implanting the Pyrocarbon Humeral Head. Subjects will exit the study after the 24 month assessments are complete.

Subjects who are enrolled but become screen failures intra-operatively (prior to the implant attempt) will have the reason for screen failure documented and then will be followed annually to collect any available safety information. Subjects will exit the study after the 24 month assessments are complete.

Subjects who are enrolled but become screen failures pre-operatively (prior to surgical procedure) will have the reason for screen failure documented then they will be exited from the study.

If any component of the investigational system is revised, the subject will follow the planned follow-up visits. If any component of the investigational system is permanently explanted during the course of the study, the subject will only have annual post-op visits at 12 and 24 month to gather available safety information. Revisions and explants are defined in section11.2.

	Baseline (Pre-op)	Day of Surgery (DOS)	Post-op Follow-up (5-21 days)	Follow-up 3M (69-111 days)	Follow-up 6M (159-201 days)	Follow-up 12M (323-407 days)	Follow-up 24M (688-772 days)	Follow-up Annual (if needed)
Demographics, Medical History and Indication	х							
Intraoperative Data		Х						
Subject Questionnaire	Х			Х	Х	Х	Х	х
Range of Motion	Х			X*	X*	Х	Х	Х
Strength Test	Х			X*	X*	Х	Х	Х
Pain Medications	Х	Х	Х	Х	Х	Х	Х	Х
Adverse Event Assessment		Х	х	Х	х	Х	Х	X
X-ray	Х		Х		Х	Х	Х	Х

Data collection schedule is as follows:

\*Optional

#### 9.1. Randomization

There is no randomization as this is a single arm study.

### 9.2. Blinding

There is no blinding as this is a single arm study.

### **10. Sample Size Considerations**

Statistical considerations for powering the primary endpoint include the following:

- 80% power with a one-sided 0.025 level of significance
- Non-inferiority test of one proportion
- 10% non-inferiority margin, and performance goal of 85%
- Assumed investigational system success rate of 85%
- Attrition rate of 15%

The sample size for this endpoint was calculated using SAS (Version 9.3) under a one-sided z-test of a binomial proportion. The minimum required sample size is estimated using the above list of statistical considerations. The resultant sample size under these assumptions is 133 subjects. With 15% attrition, 157 total subjects with an attempted implant are needed. Up to 190 subjects may be enrolled to account for pre and intra-operative screen failures. Enrollment will stop once 157 subjects have had an implant attempt.

## 11. Data Structure and Handling

## 11.1. Data Handling and Transfer

Data management will be undertaken by Tornier. A biostatistician from an independent CRO will either be provided access to download SAS datasets or Tornier will provide them upon request.

Programming of analysis datasets, tables, figures and listings will be conducted during the data management phase of the study. Tables, figures, and listings may be reviewed prior to final data lock for data review. Any data values requiring investigation or correction will be identified, and protocol deviations will be reviewed. The final run of outputs will take place after the data is deemed final. The study team will not have access to the analysis data sets until the final data set is available.

# 11.2. Missing Data and Censoring

The impact of missing data for the primary efficacy endpoint will be assessed by a sensitivity analysis. See the primary endpoint section for details.

No imputation for missing data will be performed on secondary endpoint data; i.e., patients missing the endpoint result at a visit or prematurely withdrawing prior to the time point at which the endpoint is measured will be excluded from the analysis of that endpoint.

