#### 12.6. Inferential Secondary Endpoints

The following secondary data will be evaluated for significant change from baseline to 24 months. Analyses will be performed on the ITT population, using all available data. The overall type I error will be controlled using the Hochberg method for adjusting for multiple comparisons, and will be tested only if the primary endpoint is met. Endpoints will be evaluated at a one-sided alpha level of 0.025.

- Constant score and Adjusted Constant score (see Section 12.6.1)
- American Shoulder and Elbow Surgeons (ASES) Score (see Section 12.6.2)
- Single Assessment Numeric Evaluation (SANE)
  - The SANE rating is determined by the by the subject's written response to the following question "How would you rate your shoulder today as a percentage of normal (0% to 100% scale with 100% being normal)?"

- EQ-5D (see Section 12.6.3)
- Pain (VAS)
  - Based on 0-10 scale
- Range of Motion
  - Forward Flexion
  - o Abduction
  - $\circ$  Internal rotation
  - External rotation
- Strength (average pull strength)
- Revision Rate

The hypothesis test for each of the above endpoints, with the exception of Pain (VAS) and revision rate, will be of the form:

H0:  $\mu \le 0$ HA:  $\mu > 0$ 

Where  $\mu$  is the mean change from baseline to 24 months (follow-up minus baseline) for that endpoint. The hypothesis test for the Pain (VAS) endpoint will be of the form:

H0:  $\mu \ge 0$ HA:  $\mu < 0$ 

Where  $\mu$  is the mean change from baseline to 24 months (follow-up minus baseline) in the VAS Pain score.

For each endpoint excluding revision rate, descriptive statistics will be provided for subjects at baseline and 24 month follow-up. The difference from baseline to 24 months will be summarized using descriptive statistics, and a paired t-test will be performed. Additionally, the 95% confidence interval will be calculated for the change from baseline.

The hypothesis test for the Revision rate will be of the form:

H0: p ≥ 13.2% HA: p < 13.2%

Where p is the proportion of subjects that had a revision in the 24 month time period. This endpoint was added based upon FDA feedback. As the sample size is already established at 133 subjects, the PG is based upon the observed revision rate from the Aequalis dataset and a non-inferiority margin of 8% that has approximately 90% power with a 1-sided alpha of 0.025 with the sample size of 133.

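### The score-based secondary endpoints rest on 24-month completers alone, leave the 3-, 6- and 12-month scores unused, and have no missing-data check; the reported improvement may be overstated if subjects doing poorly leave.

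*SAP*

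**What the plan says.** SAP 11.2 (Missing Data and Censoring) states: "No imputation for missing data will be performed on secondary endpoint data". It goes on to drop from each endpoint's analysis any subject who lacks the result at that visit or withdrew before it.

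SAP 12.6 then gives the method for every score endpoint: "The difference from baseline to 24 months will be summarized using descriptive statistics, and a paired t-test will be performed". Protocol 13.3.1.2 says the same. A 95% confidence interval for the change accompanies each test. SAP 12.6 assigns these analyses to the ITT population with whatever data are available, but a paired test needs both values, so a subject without month 24 contributes nothing.

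The data schedule (SAP 9; Protocol Table 3) collects the subject questionnaire at 3, 6, 12 and 24 months. Range of motion and strength are required at 12 and 24 months and optional at 3 and 6.

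SAP 12.5.2 plans three missing-data analyses for the primary endpoint: all missing as successes, all as failures, and multiple imputation. The 12-month Constant score is a candidate covariate in the imputation. No counterpart exists for the secondary scores. Revision rate, also inferential, is estimated by Kaplan-Meier and is outside this point.

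**The concern.** The completers' mean change estimates the mean change in all treated subjects only if missing month 24 is unrelated to the change itself. A subject with a poor 12-month score who then leaves takes that information out of the analysis, although the score helps predict the missing one. The SAP accepts that logic for the primary endpoint and gives no reason for not applying it here.

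What is at stake is the size of the reported improvement. This is a single-arm trial and the changes are tested against zero, so the tests themselves say little. Readers will use the mean change and its interval, and no comparator arm is present to absorb a dropout bias.

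**Working it through.** **The plan's own figures.** Inputs from SAP 10: "80% power with a one-sided 0.025 level of significance"; "10% non-inferiority margin, and performance goal of 85" percent; "Assumed investigational system success rate of 85" percent; "Attrition rate of 15" percent. The null rate is 0.85 − 0.10 = 0.75.

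n = [(1.960·√(0.75·0.25) + 0.842·√(0.85·0.15)) / 0.10]² = 132.07, rounded up to 133. This matches "The resultant sample size under these assumptions is 133 subjects". Then 133/0.85 = 156.5, rounded up to 157, which matches "With 15% attrition, 157 total subjects with an attempted implant are needed". The allowance is 157 − 133 = 24 subjects, or 15%. It is set for the composite endpoint. The documents give no sample size or SD for the change scores.

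**Size of the bias in general.** Completers' mean − full mean = (fraction missing) × (completers' mean change − dropouts' mean change). At 15% missing, a bias of 0.5 points needs a gap of 0.5/0.15 = 3.3 points, and a bias of 3 points needs a gap of 20.

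**Simulation of the change score.** There were 3,000 trials per scenario with N = 157 and 15% missing at month 24. These inputs are assumptions, not figures from the documents:

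- SD of the Constant change: 15, 20 or 25.
- 12-to-24-month correlation: 0.5, 0.7 or 0.85.
- Mean change 17 + 1.036 × SD, giving 32.5, 37.7 and 42.9, so that 85% reach the 17-point threshold.
- Odds ratio (OR) for missing month 24 per SD worse 12-month change: 0.5, 1, 2 or 3.

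The likelihood estimate uses the 12-month change as well. Selected results:

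| SD | Correlation | OR | Completers' bias | Likelihood bias | SE ratio (likelihood/completers) |
|---|---|---|---|---|---|
| 15 | 0.5 | 2 | +0.70 | −0.04 | 0.989 |
| 20 | 0.7 | 1 | −0.01 | −0.01 | 0.967 |
| 20 | 0.7 | 2 | +1.31 | −0.06 | 0.987 |
| 20 | 0.7 | 3 | +2.00 | +0.01 | 1.002 |
| 25 | 0.85 | 3 | +3.03 | 0.00 | 0.985 |
| 15 | 0.5 | 0.5 | −0.68 | +0.05 | 0.995 |
| 25 | 0.85 | 0.5 | −2.13 | −0.03 | 0.974 |

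With OR 2 to 3 the completers' mean is too high by 0.7 to 3.0 points, or 2% to 7% of the assumed mean change (0.70/32.5 = 2.2%; 3.03/42.9 = 7.1%). If half of the dropouts leave earlier at random (SD 20), the excess is 0.6 to 1.3 points.

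**Cross-check on the score itself.** There were 2,000 trials per scenario with SD 20, correlation 0.6 to 0.8 and 15% missing. Dropouts 10 points worse at month 12 give a bias of 0.5 to 0.9; 20 points worse gives 1.0 to 1.5. The likelihood estimate removes nearly all of it when every dropout has a 12-month score. When a third do not, 0.26 to 0.53 points remain. No range for the correlation with baseline was examined in this set, so it is a check on order of magnitude only.

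**Precision.** Under random dropout the SE ratio is √(1 − ρ²·0.15): 0.981, 0.963 and 0.944 for ρ = 0.5, 0.7 and 0.85. When poor responders leave, the simulated ratio is 0.95 to 1.01.

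**Would a test against zero flip?** Set the lower bound for all 157 to zero and solve for the 24 dropouts' mean. At SD 15: (1.96·15/√157 − (133/157)·32.5) / (24/157) ≈ −165 points. At SD 20 and 25 it is about −189 and −212. The Constant score runs from 0 to 100, so this cannot happen under these inputs.

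**The case against.** Four counter-arguments carry weight.

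*Direction.* A reader might infer that the improvement is overstated and the estimate materially less precise. The documents do not support that. Nothing in them relates attrition to outcome; random dropout gives no bias, and loss of better subjects gives an understatement of 0.7 to 2.1 points. The one hint of upward bias is that explanted subjects and failed implant attempts are followed for safety information only (SAP 9), so they may lack 24-month scores. It does not bear on unrevised subjects who simply miss the visit. The precision gain can be nil in the very scenario that produces upward bias. This objection stands and limits the point to a conditional one.

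*Number missing.* A reader might also infer that 24 of 157 subjects leave every score analysis. The 15% belongs to the composite. A subject lacking only a readable 24-month radiograph is excluded there (SAP 12.5.1) but keeps all scores, while a failed attempt counts as a composite failure with no score needed. Out-of-window 24-month data are kept (SAP 11.3). The fraction missing for each score is unknown.

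*Circularity.* In the simulation of the change score, dropout depends at most on the 12-month result, so a likelihood method must succeed. If shoulders worsen after month 12 and those subjects leave, the model stays biased. This stands, and is why a model alone is not enough.

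*Practicality.* Optional 3- and 6-month range-of-motion and strength values may be sparse, and internal rotation is graded by anatomical landmarks (Protocol 7.3), which does not suit a normal model without justification. These points shape the remedy and do not defeat it.

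It is also fair that the 12-month data are not wholly unused: SAP 12.5.1 summarises the composite components at 12 months.

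**Conclusion.** The point holds in conditional form. The secondary change scores are completers-only, the earlier scores do not enter the estimate, and no missing-data sensitivity analysis covers them. If subjects doing poorly at 12 months are likelier to miss month 24, the mean change and its interval may be overstated by roughly 0.5 to 3 points. This rests on an assumed SD of 15 to 25, correlation of 0.5 to 0.85 and up to 15% missing. The top of the range needs the widest SD, the highest correlation, strongly outcome-related dropout, and every dropout leaving after month 12. The gain in precision is 0 to 6% of the standard error, and no secondary test decision is expected to change.

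The reason to act is that the direction is unknown. A method valid when dropout depends on observed scores asks less than one that needs dropout to be unrelated to the change. This is a cheap improvement, not a flaw that threatens the trial's conclusion.

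**What to change.** In SAP 11.2 and 12.6, with Protocol 13.3.1.2 aligned:

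1. For each continuous score endpoint, take the 24-month change, its test and its 95% confidence interval from a repeated-measures model (or multiple imputation) using baseline and all collected visits. Use 3, 6, 12 and 24 months for questionnaire scores. Use 12 and 24 months, plus any optional earlier values, for Constant, range of motion and strength.
2. Name a simpler covariance structure as fallback where the optional values are too sparse for an unstructured one. State separately how internal rotation is analysed.
3. Keep the completers' paired t-test as supportive.
4. Add a delta-adjusted sensitivity analysis that makes the missing 24-month values progressively worse than the model predicts, since the model itself relies on missing-at-random.
5. State how scores from explanted subjects and failed implant attempts are handled, so that post-explant outcomes are not silently extrapolated from earlier scores.
6. Report the number missing at 24 months for each score.

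The cost is SAP wording and standard programming, with no new visits or data and no change to the primary test. The downside is reliance on missing-at-random in the main estimate and an analysis slightly harder to explain than a paired t-test.

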### **Revisions:**

A subject who has undergone a study system revision will be considered a failure for the primary efficacy endpoint. All available safety data will be included in summaries.

A revision is a procedure that adjusts or in any way modifies or removes part of the original implant configuration, with or without replacement of a component, after the initial surgery. A revision may also include adjusting the position of the original configuration. This may include removing a component of a joint implant and only replacing that single component. If a subject has revision surgery, the subject shall remain in the study and complete all required follow-up visits.

If a subject has a revision that includes permanent removal of the Pyrocarbon HH, they shall remain in the study and complete all required annual follow-up visits.

### **Outcome Questionnaires:**

In order to include patients in the analyses who were missing a small subset of responses to an outcome questionnaire, rules were implemented to maximize the number of patients with scores calculated. Missing responses are effectively imputed as 0. Specific rules for the Constant, ASES and EQ5D are located in the sections pertaining to the respective score later in this document.

# 11.3. Visit Windows

All data attributed to a time point per the CRF will be included in the analysis of that time point, regardless of whether it is out of the protocol specified window. A summary of visit-window adherence will be included in the final analysis. Unscheduled visit data will be included in adverse event and other summaries that are not specific to a time point. The table below outlines the visit windows for protocol prescribed visits.

Study Visit	Visit Window
Baseline	60 days pre-op through DOS
Post-op Follow-up	5-21 days post-op
3 Month Follow-up	90 Days post-op $\pm 21$ days
6 Month Follow-up	180 Days post-op $\pm$ 21 days
12 Month Follow-up	365 Days post-op $\pm$ 42 days
24 Month Follow-up	730 Days post-op $\pm$ 42 days
36 Month Follow-up (if needed)	1095 Days post-op $\pm$ 84 days
48 Month Follow-up (if needed)	1460 Days post-op $\pm$ 84 days
60 Month Follow-up (if needed)	1825 Days post-op $\pm$ 84 days
72 Month Follow-up (if needed)	2190 Days post-op $\pm$ 84 days

### 12. Statistical Analyses

### 12.1. General Considerations

Data will be summarized using descriptive statistics. Continuous data will be summarized using mean, standard deviation, minimum, and maximum. Where appropriate, non-parametric measures of location (e.g. median, interquartile range) may be provided. For categorical data frequencies and percentages will be provided.

The surgery date will be considered study day 1.

# 12.2. Analysis Populations

The Intent-to-Treat (ITT) population will consist of all subjects who have undergone an attempted or successful implantation of the investigational system.

The Per-Protocol (PP) population will include all subjects who have undergone successful implantation of the investigational system, completed 24 months of follow-up, and have had no major protocol violations (defined as not meeting inclusion/exclusion criteria or not being consented properly). Major protocol violations (inclusion/exclusion criteria not met or consent issues) will be determined by the inclusion/exclusion and protocol deviation data sets.

Effectiveness analyses will be performed on the ITT population. Analysis of the PP population will be used in support of the ITT analyses of the primary efficacy endpoint. The safety analysis will be performed on the ITT population.

### 12.3. Subject Disposition

Subject disposition will be presented by:

- Summary of patient accountability following the FDA guidance Clinical Data Presentations for Orthopedic Device Applications (2004).
- Summary of early withdrawal and reason for early withdrawal.

#### 12.4. Demographics and Baseline Characteristics

Demographics and baseline characteristics will be assessed by descriptive statistics. These factors will include (but not be limited to):

- Age
- Gender
- Body Mass Index (BMI)
- Medical history (including diagnosis)
- Adjusted Constant score
- Pain

### 12.5. Primary Effectiveness Analysis

### 12.5.1. Primary analysis

The primary endpoint is the rate of patient success at 24 months. A subject is a success at 24 months if:

- Their change in Constant score is  $\geq 17$  and
- They did not have revision surgery; and
- There is no radiographic evidence of system disassembly or fracture, and
- They did not have a system-related serious adverse event.

Subjects that undergo revision surgery within 24 months will be considered a primary endpoint failure at the time any component of the system is revised.

If a subject is missing the 24 month radiographic evidence assessment or Constant score component of the composite endpoint and did not have a system-related SAE or revision surgery, they will be excluded from the primary analysis due to inability to claim success or failure.

Subjects in whom an implant was attempted but the implant was unsuccessful will be included as failures in the primary analysis, regardless of the availability of 24 month radiographic evidence assessment or Constant score.

The presence of radiographic evidence of system disassembly or fracture will be assessed by independent radiologists. Discrepancies among the independent evaluations will be settled by majority rule. If the radiologists are unable to assess or the image wasn't available at 24 months, this will be considered missing data and the subject will be excluded from the primary analysis.

The non-inferiority of the test system to the performance goal will be evaluated using the 95% CI for the observed test system success rate. The study will be considered a success if the lower bound of the confidence interval is greater than 75% (85% - 10%).

The number of subjects who are successes (X) for each of the 4 individual components of the composite success endpoint, along with the number evaluated (N), will be summarized at 12 and 24 months as (X/N) and displayed with the overall success endpoint results based on data up to 12 and 24 months.

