13.2.2 Sample Size

Statistical considerations for powering the primary endpoint include the following:

- 80% power with a one-sided 0.025 level of significance
- Non-inferiority test of one proportion
- 10% non-inferiority margin, and performance goal of 85%
- Assumed success rate of 85%
- Attrition rate of 15%

The sample size for this endpoint was calculated using SAS (Version 9.3) under a one-sided z-test of a binomial proportion. The minimum required sample size is estimated using the above list of statistical considerations. The resultant sample size under these assumptions is 133 subjects with an implant attempt and evaluable endpoint data. With 15% attrition, 157 total implant attempts are needed. Up to 190 subjects may be enrolled to account for pre and intra-operative screen failures. Enrollment will stop once 157 subject have had an implant attempt.

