13.2.4 Missing Data

The impact of missing data due to loss to follow-up prior to 24 months will be assessed by sensitivity analyses. The primary endpoint analysis will be repeated once under the assumption that all missing subjects were successful, a second time under the assumption that all missing subjects were failures, as the most conservative assessment, and a third time using multiple imputation for missing values. The results of these analyses will be presented.

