### 12.5.2. Sensitivity Analysis

Two separate sensitivity analyses will be completed on the primary endpoint, outlined below:

- 1) The primary effectiveness analysis will be repeated under the assumption that all subjects with missing endpoint data were successful.
- 2) The primary effectiveness analysis will be repeated under the assumption that all subjects with missing endpoint data were failures.
- 3) The primary effectiveness analysis will be repeated using multiple imputation for missing endpoint data. The covariates that may (list not all-inclusive) be included in the multiple imputation process are: age, gender, treated shoulder, arthritis diagnosis, Constant score (baseline and 12 month), and BMI.

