### 13.1. Aequalis Data

A subset of data from the Tornier Aequalis Post-Market Outcomes Study was used to develop the performance goal for the primary endpoint hypothesis test of the current investigation. A total of 191 subjects from the post-market study had an indication similar to that of the current investigation and had endpoint status at 24 months determined. Their available data will be used in the comparison to the current investigation.

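### SAP 12.5.1 excludes some subjects as unclassifiable although one failing component already makes them failures, and a sensitivity analysis would then score them as successes; the effect is probably small

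*SAP*

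**What the plan says.** Protocol 5.1 and SAP 12.5.1 define success at 24 months by four conditions that must all hold: Constant change of at least 17, no revision, no radiographic disassembly or fracture, and no system-related serious adverse event.

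SAP 12.5.1 then deals with incomplete data. If either the X-ray assessment or the Constant score is missing, and there was no revision or system-related serious adverse event, subjects are dropped: "they will be excluded from the primary analysis due to inability to claim success or failure". A later sentence, on images that are absent or cannot be assessed, says "this will be considered missing data and the subject will be excluded from the primary analysis" and names no exception.

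Other failures are kept despite missing data. Unsuccessful attempts "will be included as failures in the primary analysis, regardless of the availability of 24 month radiographic evidence assessment or Constant score". On revisions, SAP 11.2 says: "A subject who has undergone a study system revision will be considered a failure for the primary efficacy endpoint".

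SAP 12.5.2 lists three sensitivity analyses. In the first, the primary analysis is "repeated under the assumption that all subjects with missing endpoint data were successful". The second treats all missing as failures. The third is multiple imputation; its named covariates include the baseline and 12-month Constant scores but not the 24-month score, and the list is said not to be complete. Protocol 13.2.4 has loss to follow-up in mind: "The impact of missing data due to loss to follow-up prior to 24 months will be assessed by sensitivity analyses".

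**The concern.** When success requires every component, one failing component settles the outcome. A subject with a Constant change of, say, 10 and no readable X-ray cannot become a success whatever the image would have shown. The SAP calls this subject unclassifiable. The mirror case, disassembly or fracture seen but no Constant score, is also a failure, though a rare one.

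The rule is out of line with the SAP's own handling of revisions, system-related serious adverse events and unsuccessful attempts, where a settled failure counts whatever else is missing. The image sentence, read literally, does not even exempt those.

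Two things are at stake. The rule sets the numerator and denominator of the single test that decides the trial. It also feeds the sensitivity analyses: missing = success would turn settled failures into successes, and imputing the composite could do so too. A subject lost to follow-up lacks both components and is truly undetermined, so the fault is confined to subjects who have one component but not the other.

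**Working it through.** **The plan's own figures.** One-sample z-test of 0.85 against 0.75, one-sided 0.025, 80% power:

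n = [(1.960·√(0.75·0.25) + 0.842·√(0.85·0.15)) / 0.10]² = 132.07, so 133. With 15% attrition, 133/0.85 = 156.47, so 157. Both match Protocol 13.2.2 and SAP 10. The point below changes neither.

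**How many restored failures reverse a pass.** The trial passes if the lower bound of the 95% interval exceeds 75%. The interval type is not stated, so two are shown. Restoring k failures adds k to the denominator only. The planned result is 0.85 × 133 ≈ 113 successes; 110 is the smallest passing count under both methods.

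| Successes/N | Wilson lower | Clopper-Pearson lower |
|---|---|---|
| 110/133 | 75.39% | 75.19% |
| 110/134 (k = 1) | 74.73% | 74.53% |
| 113/133 | 77.91% | 77.74% |
| 113/137 (k = 4) | 75.26% | 75.06% |
| 113/138 (k = 5) | 74.62% | 74.43% |

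One restored failure reverses a result on the pass line; five are needed at the planned rate.

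**How many are expected.** All missingness splits are assumptions. Components are taken as independent: 5% revision or system-related serious adverse event, 1% radiographic failure, and Constant failure set to give the composite rate p, so P(Constant failure) = 1 − p/(0.95 × 0.99). That is 0.0962 at p = 0.85. Unsuccessful attempts are not modelled separately. Three scenarios have mostly whole-visit loss:

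- (i) 12% whole visit, 1% Constant only, X-ray only 2% in all subjects.
- (ii) as (i), but X-ray only 2% in successes and 6% in failures.
- (iii) 10% whole visit, 2% Constant only, X-ray only 3% in successes and 9% in failures.

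Example, (i) at 85%: 157 × 0.88 × 0.95 = 131.25 subjects with a visit and no event. Constant failure with X-ray missing and Constant present: 131.25 × 0.0962 × 0.02 × 0.99 = 0.25. Mirror case: 131.25 × 0.01 × 0.01 × 0.98 = 0.01. Total 0.26.

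Simulation (200,000 trials of 157, Wilson; about 134 to 135 evaluable):

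| | (i) | (ii) | (iii) |
|---|---|---|---|
| Determined failures dropped, true 85% | 0.26 | 0.76 | 1.16 |
| Determined failures dropped, true 75% | 0.54 | 1.59 | 2.43 |
| Pass at true 75%, SAP rule | 1.5% | 2.2% | 2.6% |
| Pass at true 85%, SAP rule | 74.0% | 77.4% | 79.2% |
| Pass at true 75%, determined failures added | 1.2% | 1.2% | 1.1% |
| Pass at true 85%, determined failures added | 72.4% | 72.8% | 72.2% |

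With no whole-visit loss, 7.5% Constant loss and X-ray loss of 5% in successes against 15% or 30% in failures, the SAP rule passes 4.2% or 14.3% at a true 75%. With 7.5% X-ray and 7.5% Constant loss unrelated to outcome, it passes 1.5% at a true 75%; adding determined failures lowers the pass rate at a true 85% from 74.4% to 67.3%.

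**Sensitivity analyses.** Missing = failure classifies these subjects correctly but cannot isolate them: 113/157 = 72.0%, below 75% before any interval is taken. Limiting missing = success to undetermined subjects lowers its pass rate at a true 75% from about 12%, 16% and 19% to about 10%, 10% and 9% in (i) to (iii). Component-level imputation (6,000 trials, 20 imputations) passes about 2.1% at a true 75% and 81% to 83% at a true 85%, if its model is right (Constant missing at random).

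**The case against.** **No harm to the decision is shown.** This stands. X-ray, questionnaire, motion and strength belong to one 24-month visit (Protocol 7.4 and 7.6.6), out-of-window data are used (SAP 11.3), and images have two readers with a third to adjudicate (Protocol 7.3). Partial missingness should be limited. A reader might infer that the rule inflates the false-pass rate in the device's favour. That requires X-rays to be lost clearly more often in failures, and nothing in the documents shows it. That one failure reverses 110/133 is true of any result on a threshold.

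**Counting these failures is not neutral.** This also stands. A reader might infer that the remedy is simply to add them to the primary denominator. But subjects with a gain of at least 17 and no X-ray would still be dropped, so inclusion would depend on outcome. In all six cases (scenarios (i) to (iii) at both true rates) the SAP rule's expected rate is closer to the truth: for example 74.4% against 74.1% at a true 75% in (i), and 84.8% against 84.1% at a true 85% in (iii).

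**The benchmark may have used a similar rule.** Protocol 13.2 and SAP 7 describe subjects with two years of data or an earlier revision, and SAP 13.1 says the 191 "had endpoint status at 24 months determined". A determined failure fits that wording, but the documents do not say how a missing component was handled. Tightening only the trial arm could make the comparison unequal.

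**A low Constant change may be partly imputed.** SAP 12.6.1 scores missing items as 0, up to 20 points, which exceeds the 17-point threshold. The failure is then determined under the SAP's scoring rather than fully observed.

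**The SAP implements the protocol and discloses the rest.** Protocol 13.2.3 limits the primary analysis to available 24-month data, and the component table would show counts. The specific rules for revisions, events and unsuccessful attempts probably override the image sentence. None of this makes the stated ground correct or stops missing = success from scoring a settled failure as a success.

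**Conclusion.** The point holds as a classification error. SAP 12.5.1 calls undetermined a group whose failure follows from the SAP's own definition and scoring, and SAP 12.5.2 carries the error into missing = success and possibly into the imputation. The image sentence needs reconciling with the rules around it.

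The size is unknown and probably small: about 0.3 to 1.2 subjects at a true 85% under the assumed splits with mostly whole-visit loss, a false-pass probability of 1.5% to 2.6% at a true 75%, and five restored failures needed to reverse 113/133. These figures rest on independent components, assumed missingness and a Wilson interval. The documents support neither a claim of inflated error nor a bare addition of failures to the denominator. Severity is minor to moderate.

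**What to change.** 1. In SAP 12.5.1, define a determined failure as any subject with a failing component, whatever else is missing, taking the Constant change as scored under 12.6.1. Define an undetermined subject as one with no failing component and at least one missing component.
2. Reword the image sentence so that a missing or unreadable image makes only the radiographic component missing.
3. In SAP 12.5.2, apply all three sensitivity analyses only to undetermined subjects. Missing = failure gives the same result as now; the other two change. Impute components, using the observed 24-month Constant score, so that no determined outcome is imputed and subjects with a gain of at least 17 but no X-ray are kept.
4. Report the number of determined failures with a missing component.
5. State how goal-cohort subjects with a missing component were handled, and use the same rule for both groups.
6. State whether determined failures enter the primary analysis. If they do, report the component-level imputation beside it and state the downside: the pass rate at a true 85% falls from 74–79% to about 72% in (i) to (iii), or to about 67% with 7.5% X-ray and 7.5% Constant loss unrelated to outcome. Part of the fall in (ii) and (iii) is removal of upward bias. If they stay out, replace the stated ground for exclusion.

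The cost is SAP wording and modest programming, mainly for the component-level imputation. The 133 and 157 stay as they are. The change should be made before outcomes are examined.
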